5. CCI [REDACTED]
6. C4h CAB400 + rHUPH20 - Inj. 1 CAB 400 mg + 5000 U rHUPH20 SC Abdomen vs Week 4 post injection 1 in ATLAS/FLAIR IM Gluteal CAB 600 mg (CAB 200 mg/mL) Q4W [dose normalize to 400 mg]
7. C4h CAB200 + rHUPH20 - Inj. 1 CAB 400 mg + 5000 U rHUPH20 SC Abdomen vs Week 4 post injection 1 in ATLAS/FLAIR IM Gluteal CAB 600 mg (CAB 200 mg/mL) Q4W [dose normalize to 400 mg]

8. C5 IM Gluteal CAB 800 mg (CAB 400 mg/mL) Q12W Week 12 post injection 1 vs Week 4 post injection 1 in ATLAS/FLAIR IM Gluteal CAB 600 mg (CAB 200 mg/mL) Q4W [dose normalize to 800 mg]
9. C5 IM Gluteal CAB 800 mg (CAB 400 mg/mL) Q12W Week 12 post injection 1 vs Week 12 post injection 1 in ÉCLAIR IM Gluteal CAB 800 mg (CAB 200 mg/mL) Q12W
10. C5 IM Gluteal CAB 800 mg (CAB 400 mg/mL) Q12W Week 12 post injection 1 [Male participants only] vs Week 12 post injection 1 in ÉCLAIR IM Gluteal CAB 800 mg (CAB 200 mg/mL) Q12W

Injection 2 (CAB 400 mg/mL):

1. C1 CAB400 - Inj. 2 400 mg IM Gluteal vs Week 4 post injection 2 in ATLAS/FLAIR IM Gluteal CAB 400 mg (CAB 200 mg/mL) Q4W
2. C2 CAB400 - Inj. 2 200 mg SC Abdomen vs Week 4 post injection 2 in ATLAS/FLAIR IM Gluteal CAB 400 mg (CAB 200 mg/mL) Q4W [dose normalize to 200 mg]
3. C3 CAB400 - Inj. 2 400 mg IM Lateral Thigh vs Week 4 post injection 2 in ATLAS/FLAIR IM Gluteal CAB 400 mg (CAB 200 mg/mL) Q4W

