¹ At their meeting on 22 December 2020, the STR agreed to reduce the dose of the first injection for remaining Cohort 3 participants based on interim PK data from Cohorts 1 and 2.

² At their meeting on 22 December 2020, the STR agreed to conduct Cohort 4.

Cohort 4b	Receive CAB 300 mg given as 1 x 0.75 mL CAB 400 mg/mL formulation subcutaneous abdominal injection ³
Cohort 4h	Receive 5000 U of rHuPH20 followed by CAB 400 mg given as 1 x 1 mL CAB 400 mg/mL formulation or 1 x 2 mL CAB 200 mg/mL given as subcutaneously abdominal injection (sequential administration). ⁴
Second Injection (Week 4 ± 3 days)	
Cohort 1	Receive CAB 400 mg given as 1 x 1 mL CAB 400 mg/mL formulation or 400 mg as 1 x 2 mL CAB 200 mg/mL IM gluteal injection
Cohort 2	Receive CAB 400 mg given as 1 x 1 mL CAB 400 mg/mL formulation or 200 mg as 1 x 1 mL CAB 200 mg/mL subcutaneous abdominal injection The VSLC agreed ⁵ : Receive CAB 200 mg given as 0.5 mL CAB 400 mg/mL formulation or 100 mg as 1 x 0.5 mL CAB 200 mg/mL subcutaneous abdominal injection
Cohort 3	Receive CAB 400 mg given as 1 x 1 mL CAB 400 mg/mL formulation or 400 mg as 1 x 2 mL CAB 200 mg/mL IM lateral thigh injection
Cohort 4	Optional cohort. Receive CAB 400 mg/mL formulation (to a maximum of 1200 mg/3mL if IM or 600 mg/1.5mL if SC) or matched volume of CAB 200 mg/mL formulation if SC, and matched dose if IM. Dose determination by STR The STR agreed ⁶ : Receive CAB 200 mg given as 1 x 0.5 mL CAB 400 mg/mL formulation or 100 mg as 1 x 0.5 mL CAB 200 mg/mL subcutaneous abdominal injection
Cohort 4b	Receive CAB 300 mg given as 1 x 0.75 mL CAB 400 mg/mL formulation subcutaneous abdominal injection ³

³

CCI

⁴ rHuPH20 and CAB will be injected via a single butterfly needle. Due to a dead volume of 0.331 mL in the butterfly tube, a larger volume of CAB 200 mg/mL or CAB 400 mg/mL formulation will be required. Therefore, 1.4 mL of CAB 400 mg/mL and 2.4 mL of CAB 200 mg/mL will be used for injection and the exact doses of CAB 400 mg/mL and CAB 200 mg/mL administered will be 427.6 mg (1.069 mL) and 413.8 mg (2.069 mL), respectively.

⁵ At the VSLC meeting on 13 November 2020, it was agreed to modify the conduct of Cohort 2 based upon interim PK and safety data.

⁶ At their meeting on 22 December 2020, the STR agreed to conduct Cohort 4.

Part 2	
First Injection	

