6.1.3. Recombinant human hyaluronidase PH20 (rHuPH20)

Participants in Cohort 4h will receive rHuPH20 (5000 U) followed by CAB 200 mg/mL or 400 mg/mL formulation via subcutaneous injection via a single butterfly needle (also see Section 6.1.1.2). Due to a dead volume of 0.331 mL in the butterfly tube, a larger volume of CAB 200 mg/mL or CAB 400 mg/mL formulation will be required. Therefore, 1.4 mL of CAB 400 mg/mL and 2.4 mL of CAB 200 mg/mL will be used for injection, and the exact doses of CAB 400 mg/mL and CAB 200 mg/mL administered will be 427.6 mg (1.069 mL) and 413.8 mg (2.069 mL), respectively. Guidance regarding test drug preparation and administration is outlined in the pharmacy manual and drug administration instruction.

rHuPH20 will be supplied as ENHANZE™ Drug Product (EDP). EDP (rHuPH20) Solution for Injection, 1 mg/mL (110,000 U/mg), is supplied as a clear, colorless sterile liquid, packaged in a clear glass 2 mL vial, with a rubber stopper and aluminum over seal. Each vial of EDP contains 0.5 mL of recombinant human hyaluronidase (rHuPH20).

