Treatment comparisons for the PK pairwise and cross study historical comparison (See Section 8.1.5) will be displayed by injection using the following descriptors:

Pairwise Comparisons for AUC(0- τ), C_{max}, and C _{τ} :

Injection 1 (CAB 400 mg/mL):

1. C2 CAB400 - Inj. 1 600 mg SC Abdomen vs C1 CAB400 - Inj. 1 600 mg IM Gluteal
2. C3 CAB400 - Inj. 1 600 mg IM Lateral Thigh vs C1 CAB400 - Inj. 1 600 mg IM Gluteal
3. C2 CAB400 - Inj. 1 600 mg SC Abdomen vs C3 CAB400 - Inj. 1 600 mg IM Lateral Thigh
4. C4h CAB400 + rHUPH20 - Inj. 1 CAB 400 mg + 5000 U rHUPH20 SC Abdomen vs C4 CAB400 - Inj. 1 400 mg IM Gluteal

Injection 2 (CAB 400 mg/mL):

1. C3 CAB400 - Inj. 2 400 mg IM Lateral Thigh [participants who received 600 mg for Injection 1] vs C1 CAB400 - Inj. 2 400 mg IM Gluteal

Historical Comparisons:

Injection 1 (CAB 400 mg/mL):

1. C1 CAB400 - Inj. 1 600 mg IM Gluteal vs Week 4 post injection 1 in ATLAS/FLAIR IM Gluteal CAB 600 mg (CAB 200 mg/mL) Q4W
2. C2 CAB400 - Inj. 1 600 mg SC Abdomen vs Week 4 post injection 1 in ATLAS/FLAIR IM Gluteal CAB 600 mg (CAB 200 mg/mL) Q4W
3. C3 CAB400 - Inj. 1 600 mg IM Lateral Thigh vs Week 4 post injection 1 in ATLAS/FLAIR IM Gluteal CAB 600 mg (CAB 200 mg/mL) Q4W
4. C4 CAB400 - Inj. 1 400 mg IM Gluteal vs Week 4 post injection 1 in ATLAS/FLAIR IM Gluteal CAB 600 mg (CAB 200 mg/mL) Q4W [dose normalize to 400 mg]

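### SAP 5.1 treats both Cohort 4h arms as 400 mg although both documents state delivered doses of 427.6 mg and 413.8 mg, so pairwise item 4 is inflated by about 6.9% and historical items 6 and 7 probably by about 6.9% and 3.5%

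*SAP*

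**What the plan says.** **Delivered dose.** Protocol 6.1.3 explains the excess: "Due to a dead volume of 0.331 mL in the butterfly tube" the volume drawn up is increased, so that "1.4 mL of CAB 400 mg/mL and 2.4 mL of CAB 200 mg/mL will be used for injection". It then gives the doses "administered will be 427.6 mg (1.069 mL) and 413.8 mg (2.069 mL), respectively". The same figures stand in the synopsis dosing table (footnote 4), the Cohort 4h schedule in Protocol 1.3.4 (footnote 4), Table 2 of Protocol 6.2.1 (footnote 12) and the SAP's own Cohort 4h schedule (10.2.1, footnote 4).

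**Dose in the comparisons.** SAP 5.1 labels both Cohort 4h arms as 400 mg. Three listed comparisons use them:

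- Pairwise, Injection 1, item 4: "CAB 400 mg + 5000 U rHUPH20 SC Abdomen vs C4 CAB400 - Inj. 1 400 mg IM Gluteal". It carries no normalisation note. It covers AUC(0-τ), Cmax and Cτ.
- Historical, Injection 1, item 6: "C4h CAB400 + rHUPH20 - Inj. 1 CAB 400 mg + 5000 U rHUPH20 SC Abdomen vs Week 4 post injection 1" in ATLAS/FLAIR at 600 mg, with the bracket "dose normalize to 400 mg".
- Historical, Injection 1, item 7: "C4h CAB200 + rHUPH20 - Inj. 1 CAB 400 mg + 5000 U rHUPH20 SC Abdomen vs Week 4 post injection 1", with the same comparator and bracket.

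**Rules around them.** SAP 8.1.5.1 restricts pairwise comparisons to cohorts given equal doses by different routes, and SAP 8.1.2 limits the historical comparisons to Cτ. Protocol 10.4.2 permits, but does not require, dose-normalised parameters when administered doses differ between cohorts. SAP 8.1.1.2 defines Cmax/D, AUC/D and Cτ/D as the parameter divided by Dose, without saying whether that means nominal or delivered dose. The same section scales two Cohort 3 participants from 400 to 600 mg by a flat 50% increase.

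**The concern.** The documents know the delivered dose to four figures and then analyse a different one. In all three listed ratios Cohort 4h comes first, against a reference at a stated 400 mg (item 4) or a comparator normalised to 400 mg (items 6 and 7). Any uncorrected excess therefore pushes the ratio upward, and more participants would not remove it.

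Item 4 also fails the SAP's own entry condition, because 427.6 mg and 400 mg are not equal doses. It is the only within-study comparison listed for Cohort 4h, and it already combines a change of route with the addition of the enzyme. A dose excess makes it harder to interpret. Geometric mean ratios for Cohort 4h are among the primary endpoints, so the dose that enters them should be explicit.

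**Working it through.** **Inputs.** Dead volume 0.331 mL; volumes drawn 1.4 mL and 2.4 mL; concentrations 400 and 200 mg/mL (Protocol 6.1.3). Comparator doses: 400 mg for Cohort 4 and 600 mg for ATLAS/FLAIR (SAP 5.1). Planning SD of log concentration 0.66079, with N=8 against 579 (Protocol Table 4).

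**1. Reproduce the stated doses.** Dose = (volume drawn − dead volume) × concentration.

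- (1.4 − 0.331) × 400 = 1.069 × 400 = 427.6 mg
- (2.4 − 0.331) × 200 = 2.069 × 200 = 413.8 mg

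Both agree with the documents.

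**2. Inflation if 400 mg is used.** Factor = (delivered dose / 400)^β, where β = 1 means that exposure is proportional to dose. The SAP makes that assumption when it normalises 600 mg to 400 mg. The range of β from 0.7 to 1.3 is my assumption.

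| Arm | β = 0.7 | β = 1 | β = 1.3 |
|---|---|---|---|
| CAB 400 (pairwise item 4, historical item 6) | 1.048 | 1.069 | 1.091 |
| CAB 200 (historical item 7) | 1.024 | 1.0345 | 1.045 |

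These factors isolate the Cohort 4h excess. The scaling of the comparator from 600 mg depends separately on β.

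**3. What the bracket scales.** In every bracketed row (historical Injection 1 items 4, 6, 7 and 8; Injection 2 item 2) the target equals the labelled dose of the study arm: 400, 400, 400, 800 and 200 mg. Rows in which the labelled doses already match have no bracket. The natural reading is that the comparator is brought to the study arm's label. The comparator is then multiplied by 400/600 = 0.6667. Matching the delivered doses would need 427.6/600 = 0.7127 and 413.8/600 = 0.6897.

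**4. Size against planned precision.** Half-width = t(0.95; 585) × 0.66079 × √(1/8 + 1/579) = 0.3875, which reproduces Table 4 (0.387538, giving 0.6787 to 1.4733 around a ratio of 1.0).

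- ln(1.069) = 0.0667, and 0.0667/0.3875 = 17% of the half-width.
- ln(1.0345) = 0.0339, and 0.0339/0.3875 = 9%, taking the same N and SD for the CAB 200 arm.
- For pairwise item 4 the documents give no half-width. Assuming N=8 against 15 and the same SD, t(0.95; 21) × 0.66079 × √(1/8 + 1/15) = 0.498, and 0.0667/0.498 = 13%.

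**5. What linear normalisation leaves.** Dividing by delivered dose leaves a factor of 1.069^(β−1) in item 4. This is 1.048/1.069 = 0.980 at β = 0.7 and 1.091/1.069 = 1.020 at β = 1.3, so the residual is about 2% either way.

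**The case against.** The best defence concerns items 6 and 7. The bracket does not say which side is scaled. If both sides were brought to 400 mg, with 427.6 or 413.8 mg as the starting dose for Cohort 4h, these rows would carry no dose excess under proportionality. The 400 mg strings are introduced as display labels, and Dose in the /D parameters could mean delivered dose. This stands as an ambiguity: inflation in items 6 and 7 is the likelier result, not a certain one. It does not rescue pairwise item 4, which has no bracket.

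Two further points stand. For Cohort 4 the documents state 400 mg as 1 mL and give no dead-volume calculation for the intramuscular injection, so the contrast in item 4 is between stated doses. The shift is also small beside sampling error, and neither document ties a margin or decision threshold to a Cohort 4h ratio.

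A reader might infer more than the documents support:

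- *That every Cohort 4h parameter is affected in every row.* The historical rows use Cτ only. Cmax and AUC(0-τ) enter only through pairwise item 4, for the CAB 400 arm.
- *That the two Cohort 4h arms are compared with a 3.3% bias (427.6/413.8 = 1.033).* SAP 5.1 lists no ratio between them.
- *That scaling removes the excess exactly.* It does so only under dose proportionality, which the SAP plans to estimate in a model that excludes Cohort 4h.

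**Conclusion.** The inconsistency is real: both documents state delivered doses of 427.6 and 413.8 mg, and the SAP comparisons use 400 mg for both. Followed as written, the pairwise item 4 ratios for Cτ, Cmax and AUC(0-τ) are too high by about 6.9% under dose proportionality. The Cτ ratios in historical items 6 and 7 are too high by about 6.9% and 3.5% if only the comparator is scaled. These figures take the stated delivered doses, and Cohort 4's stated 400 mg, as correct.

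A stronger reading, that the Cohort 4h conclusions are invalid or that the analysis cannot proceed without the change, is not supported. No formal hypothesis is tested, the shifts are 9% to 17% of the planned half-width, and no conclusion has been shown to change. Severity is minor to moderate. The correction is worth making because the error is known, runs in one direction and is cheap to remove.

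**What to change.** 1. In SAP 8.1.1.2, define Dose for Cohort 4h as the stated delivered dose: 427.6 mg (CAB 400 mg/mL) or 413.8 mg (CAB 200 mg/mL).
2. Run pairwise item 4 on Cτ/D, Cmax/D and AUC(0-τ)/D, as Protocol 10.4.2 allows when doses differ, and reword the equal-dose condition in SAP 8.1.5.1 to match.
3. In historical items 6 and 7, normalise the comparator to 427.6 mg and 413.8 mg respectively. Alternatively, state that both sides are scaled to 400 mg, starting from delivered dose for Cohort 4h. The two are equivalent under linear scaling.
4. Footnote the Cohort 4h columns with the delivered dose. Ratios on nominal dose may be shown as well, if labelled as such.

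The cost is a few lines of SAP text and constants in the analysis program, with no new data. The change reconciles the nominal and delivered figures for analysis only and says nothing about which dose should be given.

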10.2. Sample Size Determination

In Part 1, 80 participants in Cohorts 1-4 will be randomly assigned study intervention (CAB 400 mg/mL or AC CAB 200 mg/mL), 24 participants in Cohort 4b will receive study intervention with CAB 400 mg/mL, and approximately 20 participants in Cohort 4h will be randomly assigned study intervention rHuPH20 with CAB 400 mg/mL or CAB 200 mg/mL, such that approximately 93 evaluable participants will be receiving CAB (15 in each of Cohorts 1-4 and Cohort 4h, 18 in Cohort 4b). In Part 2, 22-44 participants will be enrolled to Cohort 5 and 6 (if conducted) and randomly assigned study intervention (CAB 400 mg/mL or AC CAB 200 mg/mL) such that approximately 16 evaluable participants receiving CAB from each cohort complete the study.

With the determined sample size, certain statistical precision can be achieved when estimating PK trough concentrations using sample geometric mean trough concentration as shown below in [Table 3](#):

Table 3 Statistical Precision When Estimating PK Trough Concentration

Exp. Arm	Time Point	Assumptions*			Precision+ when estimating trough Concentration 90%CI	
		Mean (LgConc.)	SD (LgConc.)	True Geo. Mean (To be observed)		
Cohorts 1-4: 600 mg - >400 mg Q4W (N=15)	Week 4	0.3291	0.66079	1.3898	1.0290	1.8769
	Week 8	0.6123	0.47376	1.8446	1.4871	2.2881
Cohort 4h: 400 mg Q4W (N=8)	Week 4	0.3292	0.66079	1.3898	0.8927	2.1636
Cohorts 5/6: 1200 mg Q3M (N=16)	Week 12	0.0311	0.59603	1.0316	0.7944	1.3395
	Week 24	-1.3837	1.11507	0.2507	0.1538	0.4086

*Assumptions for Q4W arm were from pooled PK Trough data from FLAIR (Study 201584) and ATLAS (Study 201585) i.e. 1.44 µg /mL; assumptions for Q3M were from simulated PK Trough data from a single 1200 mg dose in 80% male and 20% female.

+Precisions were calculated based on t-distribution.

In addition, the bioavailability of CAB 400 mg/mL formulation administered IM to *gluteus medius* will be assessed relative to IM administration to lateral thigh or SC administration to abdomen from Q4W cohorts of Part 1. Additionally, C_τ following

CAB 400 mg/mL formulation administration in Part 1 will be compared to historical PK data of CAB 200 mg/mL using cross-study comparisons.

Table 4 Statistical Precision When Estimating Ratio of PK Trough Concentration

Exp. Arm	Time Point	Assumptions*			Precision* for estimating Ratio of Trough Concentration		
		CVb%	SD (LgConc.)	Ratio of Geo. Mean Concentration (To be observed)	Half Width of (Δ Lg Conc).	90% CI for Ratio	

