5. CONSIDERATIONS FOR DATA ANALYSES AND DATA HANDLING CONVENTIONS

5.1. Study Treatment & Sub-group Display Descriptors

In general, the following treatment group descriptors will be presented in data displays for reporting, with minor variations depending on whether a display is presenting treatment group information as a column or row.

For Cohort 4b, all data will be summarized by period (OLI, injection 1, injection 2, follow-up, overall) and selected safety and patient reported outcome endpoints will also be summarized by CCI PK concentrations and parameters will also be summarized by treatment sequence and period, as appropriate.

Treatment Group Descriptions					
		Randomization		Data Displays for Reporting	
Part	Arm	Code	Description	Description	Order in TLF
Part 1	C1 CAB 400	A1	CAB 400 mg/mL IM injections 4-weeks apart in gluteus muscle (cohort 1)	Oral CAB 30 mg QD	1
				Inj.1 600 mg IM Gluteal	2
				Inj.2 400 mg IM Gluteal	3
				Follow-up	4
				Overall ¹	5
	C1 CAB 200	C1	CAB 200 mg/mL IM Injection 4-weeks apart in gluteus muscle (cohort 1)	Oral CAB 30 mg QD	6
				Inj.1 600 mg IM Gluteal	7
				Inj.2 400 mg IM Gluteal	8
				Follow-up	9
				Overall ¹	10
	C2 CAB 400	A2	CAB 400 mg/mL SC injections 4-weeks apart in abdomen (cohort 2)	Oral CAB 30 mg QD	11
				Inj.1 600 mg SC Abdomen	12
				Inj.2 200 mg SC Abdomen	13
				Follow-up	14
				Overall ¹	15
	C2 CAB 200	C2	CAB 200 mg/mL SC injections 4-weeks apart in abdomen (cohort 2)	Oral CAB 30 mg QD	16
				Inj.1 300 mg SC Abdomen	17
				Inj.2 100 mg SC Abdomen	18
				Follow-up	19
				Overall ¹	20
	C3 CAB 400	A3	CAB 400 mg/mL IM injections 4-weeks apart in	Oral CAB 30 mg QD	21
				Inj. 1 600 mg IM Lateral Thigh	22
				Inj. 1 400 mg IM Lateral Thigh	23

			lateral thigh (cohort 3)	Inj. 2 400 mg IM Lateral Thigh	24
				Follow-up	25
				Overall ¹	26
	C3 CAB 200	C3	CAB 200 mg/mL IM injections 4- weeks apart in lateral thigh (cohort 3)	Oral CAB 30 mg QD	27
				Inj.1 600 mg IM Lateral Thigh	28
				Inj.1 400 mg IM Lateral Thigh	29
				Inj.2 400 mg IM Lateral Thigh	30
				Follow-up	31
				Overall ¹	32
	C4 CAB 400	A4	CAB 400 mg/mL Injections 4-weeks apart (first IM injection in gluteus medius and second SC injection in abdomen; cohort 4)	Oral CAB 30 mg QD	33
				Inj.1 400 mg IM Gluteal	34
				Inj.2 200 mg SC Abdomen	35
				Follow-up	36
				Overall ¹	37
	C4 CAB 200	C4	CAB 200 mg/mL Injections 4-weeks apart (first IM injection in gluteus medius and second SC injection in abdomen; cohort 4)	Oral CAB 30 mg	38

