				Inj.1 400 mg IM Gluteal	39
				Inj.2 100 mg SC Abdomen	40
				Follow-up	41
				Overall ¹	42
	C4b CAB 400 + Topical Steroid or NSAID 4	A4bG1	CAB 400 mg/mL Injections 4- weeks apart in CCI	Oral CAB 30 mg QD	43
				CCI	44
				CCI	45
				Follow-up	46
				Overall ¹	47
	C4b CAB 400 + Topical Steroid or NSAID 4	A4bG2	CAB 400 mg/mL Injections 4- weeks apart in CCI	Oral CAB 30 mg QD	4833
				CCI	49
				CCI	50
				Follow-up	51
				Overall ¹	52
		A4h		Oral CAB 30 mg QD	53

	C4h CAB 400 + rHUPH20		CAB 400 mg/mL Injection in the abdomen with rHuPH20	Inj. 1 CAB 400 mg + 5000 U rHUPH20 SC Abdomen	54
				Follow-up	55
				Overall ¹	56
	C4h CAB 200 + rHUPH20	A4h	CAB 200 mg/mL Injection in the abdomen with rHuPH20	Oral CAB 30 mg QD	57
				Inj. 1 CAB 400 mg + 5000 U rHUPH20 SC Abdomen	58
				Follow-up	59
				Overall ¹	60
	N/A	N/A	Pooled Group ²	Pooled Oral CAB 30 mg QD OLI ONLY	61
				Pooled Oral CAB 30 mg QD	62
				Pooled CAB 400 mg/mL Q4W 400 mg IM Gluteal	63
				Pooled CAB 200 mg/mL Q4W 400 mg IM Gluteal	64
				Pooled CAB 400 mg/mL Q4W 200 mg SC	65
				Pooled CAB 200 mg/mL Q4W 100 mg SC	66
				Pooled CAB 400 mg/mL Q4W 400 mg Lateral Thigh	67
				Pooled CAB 200 mg/mL Q4W 400 mg Lateral Thigh	68
Part 2	C5 CAB 400 ³	A5	CAB 400 mg/mL IM injections 12-weeks apart in gluteus muscle (cohort 5)	Oral CAB 30 mg QD	69
				Inj. 1 800 mg IM Gluteal	70
				Follow-up	71
				Overall ¹	72
	C5 CAB 200	C5	CAB 200 mg/mL IM injections 12-weeks apart in gluteus muscle (cohort 5)	Oral CAB 30 mg QD	73
				Inj. 1 400 mg IM Gluteal	74
				Follow-up	75
				Overall ¹	76
	N/A	N/A	Historical Data, CAB 200 mg/mL	(ATLAS/FLAIR) Inj. 1 CAB 600 mg IM Gluteal ³	77
				(ATLAS/FLAIR) Inj. 2 CAB 400 mg IM Gluteal ³	78
				(ÉCLAIR) Inj. 1 CAB 800 mg IM Gluteal ³	79

Note: A1 = Active Drug in Cohort 1; A2 = Active Drug in Cohort 2; A3 = Active Drug in Cohort 3; A4 = Active Drug in Cohort 4; A4h = Active Drug in Cohort 4h; A5 = Active Drug in Cohort 5; A6 = Active Drug in Cohort 6; C1 = Cohort 1, C2 = Cohort 2, C3 = Cohort 3, C4 = Cohort 4, C4b = Cohort 4b, C4h = Cohort 4h, C5 = Cohort 5.

1. Overall group is not applicable for PK analyses.
2. Pooled active and AC groups are only applicable when there is more than one cohort at the stated dose (mg) to combine for the specific summary.
3. Historical data for formulation of 200 mg/mL from the Phase 3 program, only applicable for PK analyses.

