8.1.1.2. Derived Pharmacokinetic Parameters

Pharmacokinetic parameters will be calculated by standard non-compartmental analysis according to current working practices and using the currently supported version of WinNonlin (8.0 or higher). All calculations of non-compartmental parameters will be based on actual sampling times. Pharmacokinetic parameters listed will be determined from the plasma concentration-time data from OLI and Injection phases, as data permit.

Parameter	Parameter Description	OLI Phase	Injection Phase
C _{max}	Maximum observed plasma concentration determined directly from the concentration-time data.	Day 1	For Injection 1 and 2 in Part 1 and Part 2
C _{max} /D	Dose normalized C _{max} , calculated as C _{max} /Dose	Day 1	For Injection 1 and 2 in Part 1 and Part 2
t _{max}	Time of C _{max} determined directly from the concentration-time data.	Day 1	For Injection 1 and 2 in Part 1 and Part 2
AUC(0-t)	Area under the concentration time curve from time zero to last quantifiable time point calculated using the linear trapezoidal rule for each incremental trapezoid and the log trapezoidal rule for each decremental trapezoid.	Day 1	For Injection 1 & 2 in Part 1 and Part 2
AUC(0-t)/D	Dose normalized AUC(0-t), calculated as AUC(0-t)/Dose	Day 1	For Injection 1 & 2 in Part 1 and Part 2
AUC(0-τ)	Area under the concentration time curve from time zero to tau time point calculated using the linear trapezoidal rule for each incremental trapezoid and the log trapezoidal rule for each decremental trapezoid. Tau=24 hours for OLI Day 1 Tau is 4 weeks for Cohort 1-4, 4b and 4h Tau is 12 weeks for cohort 5	Day 1	For Injection 1 & 2 in Part 1 and Part 2
AUC(0-τ)/D	Dose normalized AUC(0-τ) calculated as AUC(0-τ)/Dose	Day 1	For Injection 1 & 2 in Part 1 and Part 2

Parameter	Parameter Description	OLI Phase	Injection Phase
AUC(0-4) Cohort 5 only	Area under the concentration time curve from time zero to Week 4 calculated using the linear trapezoidal rule for each incremental trapezoid and the log trapezoidal rule for each decremental trapezoid.	NA	Injection 1 Part 2 (Cohort 5) (this parameter is used in the dose proportionality analysis).
AUC(0-∞)	Area under the concentration time curve from time zero to infinity	NA	For Injection 1 (Cohort 4h) & 2 in Part 1 and Part 2
AUC(0-∞)/D	Dose normalized AUC(0-∞), calculated as AUC(0-∞)/Dose	NA	For Injection 1 (Cohort 4h) & 2 in Part 1 and Part 2

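### The Cohort 2 Injection 2 comparison with history halves a trough that is about half carry-over, so its no-difference value is about 1.44 to 1.50, not 1

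*SAP*

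**What the plan says.** SAP 5.1 lists Cohort 2 on CAB 400 mg/mL as "Inj.1 600 mg SC Abdomen" followed by "Inj.2 200 mg SC Abdomen". The historical rows of the same table show the same 600 mg start ("ATLAS/FLAIR) Inj. 1 CAB 600 mg IM Gluteal") followed by 400 mg. Item 2 of the Injection 2 historical list compares the Cohort 2 trough four weeks after its second injection with "Week 4 post injection 2 in ATLAS/FLAIR IM Gluteal CAB 400 mg (CAB 200 mg/mL) Q4W [dose normalize to 200 mg"].

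SAP 8.1.1.2 defines dose-normalised parameters as the parameter divided by the dose. This includes the trough and, for example, "Dose normalized AUC(0-∞), calculated as AUC(0-∞)/Dose". No term allows for an earlier injection. A note in that section adjusts two Cohort 3 participants from 400 mg to 600 mg by a flat 50% increase, which is also simple proportional scaling. Neither document describes a carry-over correction.

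The trough compared with historical CAB 200 mg/mL data is a primary endpoint (Protocol 3, SAP 2.2). Protocol 10.4.2 specifies the Week 8 historical comparison and mentions dose normalisation only for pairwise comparisons within the study. It does not say whether the historical comparison is to be normalised.

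**The concern.** Proportional scaling of a trough is valid when all the drug measured came from the dose being scaled. Four weeks after a second long-acting injection that is not so, because drug from the first injection is still being absorbed. Here the first dose is 600 mg in both groups, so its remainder should be left alone. Halving the total makes the reference too low and moves the ratio above 1 even when the products behave identically.

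The Injection 2 pairwise row is limited to "C3 CAB400 - Inj. 2 400 mg IM Lateral Thigh [participants who received 600 mg for Injection 1"], which matches the first-injection dose, although the SAP does not give carry-over as the reason. The corresponding historical row, "C3 CAB400 - Inj. 2 400 mg IM Lateral Thigh vs Week 4 post injection 2 in ATLAS/FLAIR", has no such limit.

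These data are intended to bridge to Phase 2b studies (Protocol 2.1). A ratio near 1.5 with an interval excluding 1 could be read as higher SC exposure after Injection 2 when it comes from the scaling rule.

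**Working it through.** **Inputs.** Protocol Table 3 gives a geometric mean trough of 1.3898 µg/mL at Week 4 (log mean 0.3291, SD 0.66079) and 1.8446 µg/mL at Week 8 (log mean 0.6123, SD 0.47376). Its footnote gives the source: "Assumptions for Q4W arm were from pooled PK Trough data from FLAIR (Study 201584) and ATLAS (Study 201585"). The Week 8 comparison in Table 4 uses N=15 against 577. Doses are from SAP 5.1.

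**Reproducing the plan's figures.** exp(mean ± t × SD/√15) gives 1.3897 (1.0290, 1.8769) and 1.8447 (1.4871, 2.2882). The Week 8 log half-width, t(590 df) × 0.47376 × √(1/15 + 1/577), is 0.2041. All agree with Tables 3 and 4 to within rounding.

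**Splitting the historical Week 8 trough.** Let f4 and f8 be the trough per mg at 4 and 8 weeks after an injection. Under linear superposition:

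- f4 = 1.3898/600 = 0.0023163
- second dose: 400 × f4 = 0.927
- carry-over from the first dose: 600 × f8 = 1.8446 − 0.9265 = 0.918, which is 50% of the trough

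**Cohort 2 with an identical profile.** 200 × f4 + 600 × f8 = 0.463 + 0.918 = 1.381 µg/mL.

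| Reference | µg/mL | Ratio under identical PK |
|---|---|---|
| SAP: 1.8446 × 200/400 | 0.922 | 1.381/0.922 = 1.50 |
| Un-normalised | 1.845 | 1.381/1.845 = 0.75 |
| Scale Injection 2 part only: 1.8446 − (200/600) × 1.3898 | 1.381 | 1.00 |

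Doubling the Cohort 2 trough instead of halving the historical one gives the same 1.50.

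**Interval.** The standard error of the log ratio is 0.47376 × √(1/15 + 1/577) = 0.1239. The unequal-variance model in SAP 8.1.5.1 gives about 14.7 degrees of freedom (Satterthwaite, equal SDs assumed) and t = 1.755, so the half-width is 0.217. Then 1.50 × exp(±0.217) = 1.21 to 1.86. With the protocol's 0.204 it is about 1.22 to 1.84. Both exclude 1.

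**Sensitivity.** With r = f8/f4, the ratio is (200 + 600r)/(200 + 300r). It equals 1 only when r = 0 and cannot exceed 1.6 while f8 ≤ f4. Table 3 gives r = 0.66.

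- Using the footnote's 1.44 µg/mL for Week 4: 1.48.
- Using the decay in Table 3's single 1200 mg simulation (1.0316 to 0.2507 over 12 weeks, half-life 5.9 weeks, r = 0.62): 1.48.
- Geometric means do not add exactly. Arithmetic means give 1.44. Lognormal simulations, with assumed carry-over log SD 0.2 to 0.5 and correlation −0.3 to 0.6, give 1.44 to 1.48.
- Varying the two historical means within their sampling error: 1.45 to 1.54.

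**Cohort 3 historical row.** A participant given 400 mg first would have an expected trough of 0.918 × 400/600 + 0.927 = 1.539, a ratio of 0.834 (log −0.181). Two such participants among 15 to 18 shift the log mean by −0.181 × 2/15 to −0.181 × 2/18, about −2%.

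**The case against.** The strongest reply is that this is one descriptive row whose label discloses the normalisation. No hypothesis is tested (Protocol 10.1, SAP 2.4). Cohort 2 is compared at a matched 600 mg after Injection 1 with ATLAS/FLAIR, Cohort 1 and Cohort 3. Those three rows involve no earlier injection and carry the main evidence on SC exposure. Regimen selection may also draw on population PK modelling. All of this stands and limits the consequence, but it does not make the row correct.

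A reader might infer more than the documents support:

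- **That SC dosing as a whole would look 50% better than it is.** The Injection 1 rows are untouched, so the distortion is confined to this row.
- **That equal bioavailability alone yields 1.5.** It does not. Equal extent with a different SC release rate would change the number. The calculation needs the same dose-normalised time profile and linear PK.
- **That the protocol rules out normalising against history.** Protocol 10.4.2 is silent on this.
- **That removing the bracket alone cures the problem.** The un-normalised ratio has a value of 0.75 under identical PK. With the same half-width its interval is about 0.60 to 0.93, which also excludes 1.
- **That the Injection 2 parameters divided by dose are a comparable fault.** They also contain carry-over, but no listed Injection 2 comparison uses dose-normalised Cmax or AUC. They are descriptive summaries.

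Subtracting a residual projected at each participant's KALA would be a poor remedy, because no historical KALA is described in the SAP.

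**Conclusion.** The row is wrong as written. It applies a second-dose ratio to a trough of which about half came from an equal first dose. Under identical linear PK the planned ratio would be about 1.44 to 1.50 instead of 1.0. The upper figure comes from adding geometric means directly, and the lower from arithmetic means and the simulations.

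The size rests on superposition, on the Table 3 troughs representing the ATLAS/FLAIR data to be used, and on negligible oral lead-in residue. The direction needs less: under linear PK with identical profiles, any carry-over puts the ratio above 1. The result is a misleading point estimate and interval for one primary-endpoint comparison, not an error-rate problem. The Cohort 3 restriction and the Injection 2 dose-normalised summaries are minor matters of consistency and labelling.

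**What to change.** In item 2 of the Injection 2 historical list, replace the normalisation instruction with a reference that scales only the second dose: historical Week 4 post-Injection 2 trough minus (200/600) × historical Week 4 post-Injection 1 trough. On the Table 3 values this is 1.8446 − 0.4633 = 1.381 µg/mL, with a ratio of 1.0 under identical PK. State linearity as an assumption. If the subtraction is done per participant, say how a missing first trough or a non-positive result is handled, since the model works on logs.

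Otherwise, report the un-normalised ratio, label it with both dosing histories (600 then 200 mg; 600 then 400 mg), and state that its value under identical PK is about 0.75.

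Two smaller edits: footnote the Injection 2 dose-normalised parameters as including carry-over from Injection 1, and apply to the Cohort 3 Injection 2 historical row the 600-mg-first restriction already used in the pairwise row.

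The cost is SAP wording and a modest programming change. Both historical troughs are already used in the planned comparisons, so no new data are needed.
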